#### **POCUS versus SUM**

#### 5.2. Outcome

The primary outcomes will be the acceptability and feasibility of point-of-care ultrasound to patients. This will be assessed as:

- 1) The number of patients approached who agree to participate (objective 1)
- 2) The response rate to the questionnaire (objectives 2 and 3)
- 3) The number of patients willing to undergo POCUS scans in the future as determined by the questionnaire responses (objective 2)
- 4) The number of unblinding episodes that occur (objective 4)

The exploratory outcomes will investigate the reliability and validity of the point-of-care ultrasound device. This will be assessed as:

- 1) For categorical data, Kappa coefficients demonstrating 90% agreement or greater (objectives 1 and 2)
- 2) For numerical data, ICC 0.9 or greater (objectives 1 and 2)
- 3) For continuous data (fetal biometric measurements), high level of agreement with Bland Altman, defined as ≥95% of the differences between the two measurement methods fall within the clinically acceptable range of ±3 to ±7 mm, depending on gestational age (objectives 1 and 2)
- 4) The difference in the mean time taken to perform each type of scan (POCUS and SUM) (objective 3)
- 5) The number of patients in whom fetal assessment could not be performed (objective 2)
- 6) Data from the feasibility study will inform the sample size calculation for the full randomized controlled trial by providing estimates of outcome variability, effect size, and recruitment parameters necessary for a power analysis (objective 4)

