### 6. STUDY DESIGN AND METHODS OF DATA COLLECTION

This will be a feasibility study involving both qualitative and quantitative data developed in line with current guidance (19, 20). This feasibility study has been designed to establish the feasibility and acceptability of a future randomised controlled trial (RCT). It will involve pseudo-anonymised data collection from pregnant patients. This study will not involve an alteration to the standard care of enrolled patients.

Participants will undergo ultrasound with POCUS with a probe frequency of 3-5 MHz. The same probe model (Vscan Air CL, GE Voluson, available for routine clinical use for presentation scanning at LWH) will be used for all POCUS scans to limit variability in image quality. This model utilises a personal mobile device or tablet for image display and saves images which can be uploaded to a secure server. Measurements of fetal head circumference (HC), abdominal circumference (AC), and femur length (FL) will be taken with both devices and incorporated into the Hadlock EFW calculation. (21). Patients will also undergo ultrasound with a standard ultrasound machine (standard care). While performing the standard ultrasound, the PI will be blinded to the measurement value by covering the area of the screen where the measurement number appears with an opaque card. Both scans will be performed by the same sonographer (study PI) to limit inter-observer variability. The results of these scans will be examined using the statistical analysis as detailed below. Time taken to obtain measurements will be obtained for both methods and compared.

Clinical data will also be collected. This will consist of maternal and fetal details including maternal body mass index (BMI), antenatal risk factors, and the gestational age at the time of the scan.

Ultrasound findings and clinical measurements to be collected prospectively are illustrated in Appendix 1.

The qualitative component will address the primary objective and secondary objective 4. Participants will be asked to fill in an experience questionnaire following the ultrasounds. This questionnaire will evaluate their perception/satisfaction with the POCUS scan. Data for the qualitative component assessing acceptability will be obtained from the responses to the questionnaire. Participants will be provided either a paper-based or online questionnaire hosted at RedCap

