#### 10. STATISTICS AND DATA ANALYSIS

### 10.1 Sampling

All pregnant patients attending Liverpool Women's Hospital Trust (diabetes antenatal clinic, fetal medicine unit growth clinic, maternity assessment unit with reduced fetal movements, admitted in antenatal ward with reduced fetal movements) will be considered to take part in this study.

As this is an exploratory study and no hypothesis testing is planned a formal sample size calculation has not been performed.

We will aim to include 60 patients per cohort. There will be three cohorts, so the total number of patients will be 180, and the number of scans performed 360. The sample size estimation was determined by the study team including the statistician because this is an exploratory study with a binary primary outcome (acceptable vs non-acceptable). A review of feasibility studies by Totton et al. (22) evaluated three studies of sample size estimations. The most recent of these studies was by Teare et al. (23), who recommend 60 participants per arm for feasibility studies with binary outcomes. 60 participants per cohort will generate sufficient results for feasibility and acceptability to achieve the proposed outcomes.

This sample size will also provide sufficient data for analysis of the secondary outcomes. As these are concerned with the level of agreement between the two ultrasound modalities, we will use Bland-Altman limits of agreement. Studies using this method rarely include sample size calculations, with an average sample size of 65.(24) The overall assessment of the devices from the combined three groups will involve a total sample of 180 paired scans.

Diabetes: The Diabetes antenatal clinic at LWH runs once a week on Tuesdays and sees between 20-40 patients per week. During a six-month period, this will equate to around 750 patients.

SGA: The Growth clinics at LWH run twice a week on Mondays and Thursdays and see roughly six patients per clinic. During a six-month period, this will equate to around 300 patients.

RFM: Patients present with RFM regularly to MAU at LWH. Around four patients per day will present. In a six-month period, this will equate to around 700 patients. The PI will aim to recruit from this clinical area weekly on Fridays.

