### 10.2 Data Analysis

### Data analysis and statistical analysis plan

Data arising from the questionnaires will be analysed in Microsoft Excel and will be reported using descriptive summary statistics, mean, medians, and counts (i.e. "54% of participants were satisfied with the POCUS scan").

Acceptability will be assessed using descriptive summary statistics, mean, medians, counts, and corresponding measures of variability.

Data will be analysed using SPSS (Statistical Package for the Social Sciences, IBM, Armonk NY).

The statistical methods have been chosen in collaboration with and at the advice of a University of Liverpool statistician ([name]) to ascertain agreement between the two methods of scanning (POCUS and SUM), and to enable appropriate statistical analysis of the proposed sample. Within each group we will use interclass correlation coefficients (ICC) and Spearman correlation coefficients (SCC) to check how closely the two methods agree by looking at the agreement between the paired measurements. Intraclass correlation coefficients measure how similar the measurements from the two methods are, indicating reliability or consistency for continuous variables. As the ICC approaches 1 (0.9 or greater), the greater the level of agreement. For this study, an ICC of 0.9 or greater will be considered a high level of agreement and indicate

increased reliability of the Vscan device.

To assess for difference in the scan duration, the mean scan time, median and interquartile ranges will be used. We will examine for correlation between the continuous variables of BMI and scan time with both POCUS and standard ultrasound. Calculation of a correlation coefficient will be performed with Spearman's correlation test.

Kappa coefficients measure agreement for categorical outcomes, such as assessments of fetal presentation or amniotic fluid levels. Values  $\leq 0$  indicate no agreement, 0.01–0.20 as none to slight, 0.21–0.40 as fair, 0.41–0.60 as moderate, 0.61–0.80 as substantial, and 0.81–1.00 as almost perfect agreement. These methods will be used to check for similarity within the methods (POCUS or SUM). This will ensure the measurements taken by the methods themselves are consistent.

Calculating the mean difference and 95% confidence intervals will provide estimate of any offset between two devices. Bland-Altman plots with limits of agreement will also provide a visual indication of the level of agreement between the two devices.

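### Scan time is recorded in pairs but compared only through device means, medians and IQRs; no within-patient difference, spread or interval is named for it

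*Protocol*

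**What the plan says.** Section 6 sets up a paired design: "Both scans will be performed by the same sonographer (study PI) to limit inter-observer variability". On duration it adds: "Time taken to obtain measurements will be obtained for both methods and compared". The data collection appendix (14.1) lists scan duration as a field for each device. Section 10.1 describes the pooled data as pairs: "The overall assessment of the devices from the combined three groups will involve a total sample of 180 paired scans".

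Exploratory outcome 4 in section 5.2 is "The difference in the mean time taken to perform each type of scan (POCUS and SUM) (objective 3". Section 10.2 gives the method: "To assess for difference in the scan duration, the mean scan time, median and interquartile ranges will be used". It also plans a Spearman correlation of BMI with scan time on each device, which does not compare the devices.

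Elsewhere in section 10.2 a mean difference with a 95% interval is planned for a systematic offset between the devices. That sentence stands beside the Bland-Altman plots and does not name duration. The paragraph that closes these methods gives their purpose as checking fetal measurements.

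Exploratory outcome 5 is "The number of patients in whom fetal assessment could not be performed (objective 2". Nothing says what happens to the scan time of such a patient.

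**The concern.** Efficiency is exploratory objective 3, and this is its main device comparison. BMI, gestation and fetal position probably affect both scans of the same patient. The IQR of each device's times includes that shared variation, which cancels in the within-patient difference. Two overlapping IQRs therefore say little about whether one device is consistently quicker, and the protocol names no interval for the time difference that would say more.

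The second issue is incomplete pairs. A difference of device means compares like with like only if both means cover the same patients. The plan expects some patients who cannot be assessed but does not tie them to the time comparison. If one device lacks times in the difficult patients and the other does not, the comparison mixes device with case difficulty.

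**Working it through.** **Inputs.** From section 10.1: "We will aim to include 60 patients per cohort", three cohorts, and "the total number of patients will be 180, and the number of scans performed 360". The documents give no SD of scan time, no correlation between the two times and no failure rate. Results are therefore in units of the SD of scan time (taken as equal on both devices), with an assumed within-patient correlation rho of 0.3, 0.5 or 0.7.

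**1. The plan's own figures.** 3 × 60 = 180 patients; 180 × 2 = 360 scans, or 180 pairs. These reproduce. There is no scan-time figure to reproduce.

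**2. Point estimate with complete pairs.** Mean(POCUS) − mean(SUM) = mean(POCUS − SUM), exactly. Outcome 4 as defined is not biased when every patient has both times.

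**3. Spread and precision.** The SD of the within-patient difference is SD × sqrt(2(1 − rho)): 1.18, 1.00 and 0.77 SD at rho 0.3, 0.5 and 0.7. The spread on each device is 1 SD in all three cases, so per-device summaries cannot tell them apart. The 95% half-width for the mean difference is 1.96 × sqrt(2(1 − rho)/n) if paired and 1.96 × sqrt(2/n) if pairing is ignored:

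| n | Pairing ignored | Paired, rho 0.3 | Paired, rho 0.5 | Paired, rho 0.7 |
|---|---|---|---|---|
| 60 (one cohort) | 0.358 SD | 0.299 | 0.253 | 0.196 |
| 180 (all) | 0.207 SD | 0.173 | 0.146 | 0.113 |

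The ratio is 1/sqrt(1 − rho): 1.20, 1.41 and 1.83.

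**4. Medians.** The difference of two medians is not in general the median of the differences. In an illustrative log-normal case (POCUS log-mean 2.6 and log-SD 0.4; SUM 2.7 and 0.3; rho 0.5 on the log scale) the difference of medians is −1.42, the median difference −1.36 and the mean difference −0.99. The first two are close here. The point is that they are different quantities.

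**5. Times missing on one device.** Suppose there is no true difference, and a share f of patients, those highest on a difficulty factor shared by both devices, has a SUM time but no POCUS time. The difference of device means then shifts by −sqrt(rho) × phi(z)/(1 − f), where phi is the standard normal density and z the standard normal quantile at 1 − f. For f = 5%, 10% and 20%, phi(z)/(1 − f) is 0.109, 0.195 and 0.350.

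| f | rho 0.3 | rho 0.5 | rho 0.7 |
|---|---|---|---|
| 5% | −0.06 SD | −0.08 | −0.09 |
| 10% | −0.11 SD | −0.14 | −0.16 |
| 20% | −0.19 SD | −0.25 | −0.29 |

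A simulation of 1,000,000 pairs agrees, and in it the mean difference over complete pairs is 0.00.

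**6. How far complete pairs help.** Step 5 assumes failure depends only on shared difficulty. If instead the scans lost are those that would have been slowest on POCUS, then at 10% loss and rho 0.5 the shift is −0.19 SD from device means and still −0.10 SD over complete pairs. If abandoned scans stay in with a short time (assumed 5 minutes against a mean of 15 and SD of 5), the shift at 10% is −0.32 SD with or without pairing. A long recorded time for a failed scan would push the other way.

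**The case against.** The strongest reply is that nothing in section 10.2 is an unpaired method. It names summary statistics, the protocol calls its data paired, and on complete pairs the difference of means is the paired mean difference. The study is exploratory and plans no hypothesis test. The offset sentence might be stretched to cover time. Duration is recorded separately from the measurements, so a patient whose assessment fails may still have a time. Handling of incomplete pairs could sit in a separate analysis plan.

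Much of this stands, and it rules out three stronger readings. A reader might infer that the planned estimate is wrong; step 2 shows that with complete pairs it is not. A reader might infer a loss of power; the protocol specifies no test and no unpaired interval for scan time, so the widths above show what pairing can offer, not a defect in a planned test. A reader might infer that POCUS will look falsely fast; the documents do not say that POCUS alone fails, that failed scans lack a time, or how often this happens.

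The reply does not remove the point. The scan-time method is stated, under a heading that calls itself the statistical analysis plan, and it leaves out the quantity the paired design was built to give. The offset sentence is tied by its context to fetal measurements. If it was meant to cover duration, saying so would settle the precision issue but not the incomplete pairs.

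**Conclusion.** The point holds as a recommended change to an exploratory, descriptive outcome. Scan time should be analysed as a within-patient difference, and the protocol names neither that difference nor any measure of its precision. An interval that ignored pairing would be 1.20 to 1.83 times too wide for rho 0.3 to 0.7. The incomplete-pair shift, about 0.11 to 0.16 SD in favour of POCUS at 10% loss, rests on assumed values of rho and the failure share, and on failed patients lacking only a POCUS time. It is a possibility to guard against, not a predicted bias. A reader might also infer that pairing alone cures it. It does so fully only if failure depends on difficulty shared by both devices, so a rule for the time of abandoned scans is needed as well.

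**What to change.** In section 5.2, restate exploratory outcome 4 as the mean within-patient difference in scan time, POCUS minus SUM.

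In section 10.2, replace the scan-time sentence with text to this effect:

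- In patients with a completed scan time on both devices, the difference POCUS minus SUM is calculated. Its mean with a paired 95% CI, and its median and IQR, are reported by cohort and overall.
- Per-device mean, median and IQR are given for the same patients, as description only.
- The time of an abandoned or incomplete scan does not count as a completed scan time.
- The number of patients without a completed time is reported by device, beside the time result.

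The cost is a few sentences and one computed variable in SPSS, with no new patients or measurements; the record must show whether each scan was completed. The downside is small: the estimate applies only to patients completed on both devices, so it must be read with the failure counts.

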# 2. BACKGROUND

In 2021, the UK Government announced its goals to reduce stillbirth rates. (1) This led to the promotion of the Saving Babies' Lives Care Bundle (v2 at the time), a strategy by NHS England to provide a framework of assessment and management of pregnancies by risk factor, with the aim of reducing stillbirth. One of its five key interventions is risk assessment and surveillance for fetal growth restriction. (2) With the introduction of the Saving Babies' Lives Care Bundle v2 in the National Health Service (NHS), there has been an increase in the demand for antenatal ultrasound, (3) which leads to increased costs for trusts due to increased need for ultrasound machines and technicians. The total cost of implementation of the Saving Babies' Lives Care Bundle is estimated at around £27m, with ultrasound scans comprising around £9.8m of this. (3)

Three million obstetric ultrasounds are performed annually in the UK, (4) representing a significant and rising cost to the health service. Standard ultrasound imaging is currently the gold-standard for diagnosing common clinical complications such as fetal malpresentation, abnormal placentation, in-utero demise, growth disorders, and abnormalities in amniotic fluid volume. Standard ultrasound imaging requires a high-specification machine, the cost of which can be around £15 000-£60 000.(5) Specialised probes may increase the cost, as well as maintenance and software updates. Due to the complexity of these machines, suitably qualified sonographers are needed to operate them and perform the examinations. Training and retaining higher numbers of these professionals due to an increase in demand for ultrasound has associated costs.

Point-of-care ultrasound (POCUS) is an ultrasound examination performed by the clinician attending the patient that directly affects immediate management. Indications vary across specialties, but POCUS is most

commonly used in imaging-critical specialties where emergencies can be fast-paced. Obstetrics is one such specialty. POCUS has traditionally been provided through use of portable cart-based ultrasound machines, but recent developments in microtechnologies have brought about a new era of hand-held devices which fit into the clinician's pocket, increasing portability and availability.

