# **Exploratory Objectives:**

- 1) To evaluate the intraclass correlation (reliability) of hand-held POCUS for the assessment of second and third trimester fetal biometry
- 2) To assess the validity of hand-held POCUS in patients with different antenatal risk factors (SGA, Diabetes, and RFM)
- 3) To examine the efficiency of hand-held POCUS for second and third trimester assessment of fetal biometry
- 4) To determine the minimum sufficient sample size to detect a difference in measurements taken with

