These methods evaluate both quantitative and qualitative agreement across different types of data (continuous and categorical) and aim to verify if POCUS aligns with SUM in measuring fetal parameters accurately.

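### For categorical findings the validity objective rests on kappa alone, which does not separate abnormalities POCUS missed from those it over-called, although SUM is named the gold standard

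*Protocol*

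**What the plan says.** Section 5.1 separates two exploratory objectives. Objective 1 is reliability. Objective 2 is validity: "To assess the validity of hand-held POCUS in patients with different antenatal risk factors (SGA, Diabetes, and RFM").

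Section 5.2 gives both the same criterion for categorical findings: "For categorical data, Kappa coefficients demonstrating 90% agreement or greater (objectives 1 and 2"). Section 10.2 names the statistic ("Kappa coefficients measure agreement for categorical outcomes, such as assessments of fetal presentation or amniotic fluid levels") and adds a descriptive scale whose top band reads "and 0.81–1.00 as almost perfect agreement". It closes by saying the methods "aim to verify if POCUS aligns with SUM in measuring fetal parameters accurately".

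Section 2 gives SUM the status of a reference: "Standard ultrasound imaging is currently the gold-standard for diagnosing common clinical complications such as fetal malpresentation". The same sentence goes on to placentation, in-utero demise, growth disorders and amniotic fluid.

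Sensitivity, specificity and a cross-table against SUM appear nowhere. The only other objective 2 outcome that bears on categorical findings is "The number of patients in whom fetal assessment could not be performed (objective 2"). That counts failed examinations, not findings that were seen and misread.

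**The concern.** Kappa treats the two devices as interchangeable raters. That suits reliability. For validity against a named reference there are two kinds of error: an abnormality on SUM that POCUS does not show, and an abnormality on POCUS that SUM does not confirm. Kappa merges them into one figure.

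For a device considered for routine antenatal scanning the two errors do not have the same consequences. A plan that reports only kappa cannot tell the designers of the next study which kind occurred, or how often.

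The wording of the mark makes the size of the problem uncertain. A kappa coefficient is not a percentage of agreement, so the 90% in section 5.2 can be read as kappa of at least 0.90 or as raw agreement of at least 90%. Section 10.2 adds a third, lower reference point at 0.81.

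**Working it through.** **Inputs from the protocol.** Section 10.1: 60 patients per cohort, three cohorts, each patient scanned with both devices. 3 × 60 = 180 patients and 2 × 180 = 360 scans, which reproduces the stated totals. Section 5.2: the 90% mark. Section 10.2: the band from 0.81 to 1.00. The protocol gives no prevalence for any categorical finding, so all prevalences and tables below are assumptions.

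**Notation.** With SUM as reference: *a* abnormal on both, *b* false alarms, *c* missed, *d* normal on both, *n* the total. Observed agreement is po = (a + d)/n. Chance agreement is pe = [(a + b)(a + c) + (c + d)(b + d)]/n². Kappa = (po − pe)/(1 − pe).

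**Step 1: kappa does not show direction.** Take 60 pairs, 9 abnormal on both and 48 normal on both.
- 3 missed, no false alarms: po = 57/60 = 0.95; pe = (9 × 12 + 51 × 48)/3600 = 0.71; kappa = 0.24/0.29 = 0.828. Sensitivity is 9/12 = 75%.
- 3 false alarms, none missed: the margins swap, so po, pe and kappa are the same. Sensitivity is 9/9 = 100% and specificity 48/51 = 94%.

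**Step 2: the largest share that can be missed, binary finding.** With no false alarms, prevalence p and sensitivity s, kappa = 2s(1 − p)/[s(1 − p) + 1 − ps]. As p approaches 0 this tends to 2s/(1 + s).
- Kappa 0.90 requires s ≥ 0.90/1.10 = 0.818, so at most 18.2% missed. At higher prevalence the limit tightens: 16.7% at p = 10%, 15.1% at 20%, 10% at 50%.
- Kappa 0.81 requires s ≥ 0.81/1.19 = 0.681, so at most 31.9% missed; 29.7% at p = 10%, 27.3% at 20%, 24.7% at 30%.

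**Step 3: whole-number tables at the planned sizes.** The first two readings show the largest share found in a search of tables.

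| Reading of the mark | Missed / abnormal on SUM | Pairs | Result |
|---|---|---|---|
| Kappa ≥ 0.90 | 1 / 6 (16.7%) | 60 | kappa 0.900 |
| Kappa ≥ 0.90 | 1 / 6 (16.7%) | 180 | kappa 0.906 |
| Kappa ≥ 0.81 | 2 / 7 (28.6%) | 60 | kappa 0.815 |
| Kappa ≥ 0.81 | 3 / 10 (30%) | 180 | kappa 0.815 |
| Raw agreement ≥ 90% | 6 / 6 (100%) | 60 | agreement 90%, kappa 0 |

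A fuller example at kappa ≥ 0.90: 180 pairs, 36 abnormal, 5 missed. po = 175/180 = 0.972; pe = (31 × 36 + 149 × 144)/32400 = 0.697; kappa = 0.908. Sensitivity is 31/36 = 86%, exact 95% interval 71–95%.

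**Step 4: several categories.** Assume placental site on SUM is 82 and 82 in two normal sites and 16 low, and POCUS places 8 of the 16 low placentas in the normal sites, 4 in each. po = 172/180 = 0.956; pe = (82 × 86 + 82 × 86 + 16 × 8)/32400 = 0.439; kappa = 0.516/0.561 = 0.921. Half the low placentas are missed and kappa still exceeds 0.90, because agreement between the two normal sites carries the coefficient.

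**The case against.** **The mark is stricter than it may look.** A reader might infer that POCUS can meet the criterion while missing a quarter or more of abnormal findings on any reading. The protocol does not support that. If the mark means kappa of at least 0.90, a binary finding with a quarter missed fails at every prevalence: with no false alarms kappa is 0.855 at 2%, 0.844 at 10%, 0.828 at 20% and 0.808 at 30%. With few abnormal cases kappa is unforgiving: in 60 pairs, one miss among 3, 4 or 5 abnormal findings gives 0.79, 0.85 or 0.88. A quarter missed needs the 0.81 band, the raw-agreement reading or a multi-category finding. This stands, and it limits the size of the point.

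**Nothing is decided on these outcomes.** They are exploratory, no hypothesis is tested, the primary outcomes are feasibility and acceptability, and section 6 says standard care is unaltered. A reader might infer that the plan could lead to POCUS replacing the standard scan; no such decision is attached. This also stands. The results are nonetheless meant to guide later studies (section 3).

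**It is detail for a SAP.** Kappa is computed from a cross-table, so the counts will exist, and nothing forbids reporting them. This stands only in part: section 5.2 itself fixes the measure and the mark for the validity objective.

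**Sensitivity will be imprecise and flattering.** 4 of 5 detected has an exact 95% interval of about 28–99%. One operator does both scans, and the card described in section 6 hides only measurement values, so presentation, placental site and heartbeat are known from the other scan. Both points are fair. The second affects kappa equally; the first is real uncertainty that should be shown.

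**Conclusion.** The point holds as a mismatch between measure and objective: validity against a named reference is judged, for categorical findings, by a symmetric coefficient with no measure of missed or over-called findings. That part does not depend on how the 90% mark is read.

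The size does. For a binary finding the largest share missed is about 1 in 6 at kappa 0.90, about 29–30% at kappa 0.81, and all of them under raw agreement of 90% if prevalence is 10% or less. For a multi-category finding, half the cases in one category can be missed at kappa above 0.90. These figures rest on assumed prevalences and tables and show what the criterion allows, not what is likely to occur.

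Since the outcome is exploratory, this is a cheap improvement, not a flaw that threatens the study's primary aims.

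**What to change.** In sections 5.2 and 10.2:
- Keep kappa for objective 1, and say whether the mark is on the kappa scale or is raw agreement.
- For objective 2, report for each categorical finding (presentation, amniotic fluid category, placental location, umbilical artery end-diastolic flow, fetal heartbeat) the POCUS-by-SUM table, with sensitivity and specificity against SUM and exact 95% intervals, pooled over 180 and by cohort. State in advance which categories count as abnormal; Appendix 1 lists the items without defining this.
- Where abnormal findings are few, report the number missed out of the number present.
- State that kappa alone does not support a claim of validity, and that because the same operator performs both scans with only measurement values masked, these estimates are likely optimistic.

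The cost is a few lines of text. Every item is already collected on both devices (Appendix 1), so no extra patients or scans are needed. The downside is wide intervals where abnormal findings are rare.

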# Measurements

POCUS: Fetal heartbeat, presentation, liquor volume (MVP), HC (mm), AC (mm), FL (mm), Umbilical Artery EDF, Placental location, EFW (g), Scan duration (HH:MM:SS)

SUM: Fetal heartbeat, presentation, liquor volume (MVP), HC (mm), AC (mm), FL (mm), Umbilical Artery EDF & PI, Placental location, EFW (g), Scan duration (HH:MM:SS

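### Section 10.2 promises a consistency check within POCUS and within SUM, but the protocol describes one scan per device and no repeat readings, so only between-device agreement can be estimated

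*Protocol*

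**What the plan says.** Section 10.2 introduces the ICC as a comparison of the paired POCUS and SUM measurements and kappa as agreement for categorical findings such as presentation and amniotic fluid. It then adds a further use: "These methods will be used to check for similarity within the methods (POCUS or SUM". The next sentence says that this guarantees that each method's own measurements are consistent. Earlier in the same section, an ICC of 0.9 or greater is read as a sign of greater reliability of the hand-held device.

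Exploratory objective 1 (section 5.1) has the same slant: "To evaluate the intraclass correlation (reliability) of hand-held POCUS for the assessment of second and third trimester fetal biometry".

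The data come from the following design:

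- Section 10.1: "We will aim to include 60 patients per cohort", in three cohorts, so that "the total number of patients will be 180, and the number of scans performed 360". The overall assessment "will involve a total sample of 180 paired scans".
- Section 6: "Both scans will be performed by the same sonographer (study PI) to limit inter-observer variability".
- Appendix 1 lists each item once per device, beginning "POCUS: Fetal heartbeat, presentation, liquor volume (MVP), HC (mm), AC (mm), FL (mm". The SUM list has the same form.
- Appendix 3 shows one scanning occasion.

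Nowhere does the protocol describe a repeat scan, repeat caliper placement, re-reading of stored images or a second observer.

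**The concern.** Consistency within a device is a repeatability question: does the same device give the same answer twice on the same fetus? That takes at least two readings per device in some patients. A single POCUS value paired with a single SUM value answers a different question, whether the two devices agree.

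If the text stands, two things follow. The report is committed to an assurance about each device that has no data behind it. And a between-device ICC will be credited to one device. If the limits of agreement turn out wide, the study could not say whether the scatter comes from POCUS, from the reference machine, or from a real difference between devices that varies by patient. Replicates that were not taken cannot be recovered after scanning.

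**Working it through.** **Plan's own counts (section 10.1).** 3 cohorts × 60 = 180 patients. 180 × 2 devices × 1 scan = 360 scans. Both stated figures reproduce. 360 / 180 = 2 scans per patient, one per device, which matches the 180 pairs.

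**Within-device degrees of freedom.** With N patients and m readings per device per patient, df per device = N × (m − 1).

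- As described, m = 1: 180 × 0 = 0 overall, and 60 × 0 = 0 in each cohort.
- With duplicates, m = 2: 180 × 1 = 180 overall and 60 per cohort, from 180 × 2 × 2 = 720 readings of each parameter.

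The zero needs no assumption about variability. It applies equally to an ICC, an SD and a kappa.

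**What the pairs can and cannot show.** Write each reading as true value + patient-by-device effect + repeat error, all independent. Assume a true-value SD of 20 mm (not a protocol figure) and three different splits of the error:

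| Case | POCUS patient-by-device variance | POCUS repeat variance | SUM patient-by-device variance | SUM repeat variance |
|---|---|---|---|---|
| A | 0 | 16 | 0 | 9 |
| B | 12 | 4 | 5 | 4 |
| C | 16 | 0 | 9 | 0 |

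In every case:

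- POCUS variance = 400 + 16 = 416, SUM variance = 400 + 9 = 409, and covariance = 400.
- SD of differences = √(16 + 9) = 5.0 mm.
- Between-device ICC (no offset) = 400 / (400 + 25/2) = 0.970.

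The within-POCUS ICC nevertheless differs: A 400/416 = 0.962, B 412/416 = 0.990, C 416/416 = 1.000. The paired data are the same in all three cases, so they cannot tell these cases apart. A simulation of the three cases gave the same picture apart from sampling noise.

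**Repeat error against the agreement criterion.** Section 5.2 asks for at least 95% of differences within ±3 to ±7 mm, depending on gestational age. If both devices had the same repeat SD s, no offset and no patient-by-device effect, the limits would be ±1.96 × √2 × s = ±2.77 × s. The documents give no value for s, so a range is shown:

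| Assumed s (mm) | Limits (mm) |
|---|---|
| 1 | ±2.8 |
| 2 | ±5.5 |
| 2.5 | ±6.9 |
| 3 | ±8.3 |

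Repeat error alone fills ±3 mm at s = 3 / 2.77 = 1.08 mm, and ±7 mm at s = 7 / 2.77 = 2.53 mm. Whether it matters in practice depends on s, which this design does not estimate.

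**The case against.** The best defence is that the protocol uses reliability loosely to mean agreement between methods. Section 10.2 defines the ICC on POCUS–SUM pairs, section 5.2 ties the 0.9 threshold to exploratory objectives 1 and 2, section 10.1 describes the secondary outcomes as agreement between modalities, and section 10.2 closes with whether POCUS aligns with SUM. This stands. A reader might infer that exploratory objective 1 cannot be answered at all, but the documents do not support that: 180 pairs answer it in the between-device sense. The objective is mislabelled.

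A reader might also take it as fact that only one value per parameter is recorded. One scan per device is explicit in the counts. One reading per scan is inferred from single entries in Appendix 1 and from silence, because the protocol never says so and the case report form is not shown. If duplicates are intended, they need to be written in.

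It could be argued that the within-method sentence is a slip for between. Perhaps so, but the sentence after it speaks of each method's own consistency, so the text needs correcting on either reading. A separate analysis plan could not rescue it, because it cannot supply readings that were not taken. Re-reading stored POCUS images would capture caliper error but not re-acquisition of the plane, and section 10.2 describes study storage for POCUS images only.

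Finally, paired data do allow some separation. The mean difference estimates a constant offset. Variance minus covariance gives an error variance per device if both devices share a scale and their errors are independent. In cases A to C that calculation returns 16 and 9 every time, because it lumps repeat error with patient-by-device effects. It does not yield repeatability.

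**Conclusion.** The two within-method sentences in section 10.2 claim something the described design cannot deliver: within-device df are 0 for both devices, overall and in each cohort. The only ICC and kappa available compare POCUS with SUM, in the hands of one operator. An ICC of 0.9 or greater should not be reported as reliability of the hand-held device by itself.

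Severity is moderate. The four primary outcomes, the sample size, scan time, and the between-device Bland-Altman, ICC and kappa analyses all stand.

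A reader might go further and infer that a usable device would be judged invalid because of the reference machine's repeat error. The documents do not support that. They give no repeat SD, the result changes sides across plausible inputs, and even an assumed 2.5 mm gives ±6.9 mm, which still meets the ±7 mm end of the criterion.

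The conclusion rests on one assumption: that no replicate readings are planned in a form not shown.

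**What to change.** **Wording (sufficient, nearly free).**

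- Delete the two within-method sentences in section 10.2.
- Reword exploratory objective 1, for example: *to estimate single-operator agreement between POCUS and SUM for second and third trimester fetal biometry*.
- Change the section 10.2 interpretation of an ICC of 0.9 or greater in the same way.
- Make no claim of within-device consistency in the report. The 180 patients and 360 scans stay as they are.

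**Optional, only if the team wants repeatability.** Take two independent readings of HC, AC and FL on each device, re-acquiring the plane and re-placing the calipers, and describe this in section 6, section 10.2 and Appendix 1.

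- Repeat the categorical items too if a within-device kappa is kept.
- Mask the values on POCUS as well. Section 6 describes masking only on the standard machine, and unmasked repeats by one operator would look more consistent than they are.
- Stop the scan-duration clock after the first set.

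With duplicates in every patient, the approximate relative 95% half-width for the within-device SD is 1.96 / √(2 × df): 1.96 / √360 = 10% overall and 1.96 / √120 = 18% per cohort.

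The cost is at least three extra fields per device and longer scans, by an amount the documents do not let one estimate. Because the SUM scan is standard care, the team would have to square the added time with section 6, which says that standard care is not altered.
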